1. RISKS TO THE SUBJECTS

Targeted/Planned Enrollment Table

Total Planned Enrollment 40

TARGETED/PLANNED ENROLLMENT: Number of Subjects						
	Sex/Gender					
Ethnic Category	Females	Males	Total			
Hispanic or Latino	1	1	2			
Not Hispanic or Latino	19	19	38			
Ethnic Category: Total of All Subjects*	40					
Racial Categories						
American Indian/Alaska Native	0	0	0			
Asian	1	1	2			
Native Hawaiian or Other Pacific Islander	1	1	2			
Black or African American	4	4	8			
White	14	14	28			
Racial Categories: Total of All Subjects*	20	20	40			

The most recent information reported by the South Carolina Department of Alcohol and Other Drug Abuse Services reports 49.6% of those admitted to an inpatient unit for opiate detoxification are women, and 50.4% are men. Additionally, 91% are Caucasian, 7.2% are African American, and 1.7% are of another race. We expect our recruited population to have a similar demographic make-up, with the exception of being more ethnically diverse (Charleston is more diverse than other SC counties).

We will attempt to recruit all potential participants from the community. We will not exclude anyone based on age, gender, ethnicity, or race.

Review of Adverse Events: Adverse events (AEs) will be assessed daily by study personnel. The type of AE, severity of AE, and the relationship to the application of rTMS will be recorded. AEs will be coded using Medical Dictionary for Regulatory Activities (MedDRA) rules.

Compensation and Retention: Participants will receive \$160 for completion of the acute treatment phase of the study, and \$120 for in-person completion of both the one and four-week follow-up visits. If participants elect to complete the follow-up visits by phone, they will be compensated \$60 per phone call. The total possible compensation will be \$400. Compensation will be given in the form of Greenphire MasterCard debit cards.

PROTECTION OF HUMAN SUBJECTS

1. RISKS TO THE SUBJECTS

a. Human Subjects Involvement and Characteristics

Admission into the study is open to men and women and to all racial and ethnic groups, age 18-65. Forty opiate use disordered patients will be recruited from a pool of patients admitted to an inpatient unit for detoxification. Inclusion/exclusion criteria that apply to all participants are listed below:

General Inclusion / Exclusion Criteria

Inclusion Criteria:

1: Participants must be able to provide informed consent and function at an intellectual level sufficient to allow accurate completion of all assessment instruments.

11 of 19

- 2: Participants must meet DSM-5 criteria for moderate or severe OUD. While individuals may also meet criteria for use disorders of other substances (with the exception of alcohol or benzodiazepines), they must identify prescription opiates as their primary substance of abuse.
- 3: Participants must be admitted to the inpatient unit for opiate detoxification.
- 4: Participants must consent to random assignment.

Exclusion Criteria:

- 1: Participants who are pregnant will be excluded.
- 2: Participants with a history of/or current psychotic disorder will be excluded.
- 3: Participants with a history of dementia or other cognitive impairment will be excluded.
- 4: Participants with active suicidal ideation, or a suicide attempt within the past 90 days will be excluded.
- 5: Participants with contraindications to receiving rTMS (including a history of seizures, or any implanted metal above the neck) will be excluded.
- 6: Those with unstable general medical conditions will be excluded.
- 7: Those who are currently using naltrexone, or tramadol, will be excluded.
- 8: Those with alcohol or benzodiazepine use disorders will be excluded due to increased risk of seizure.

b. Sources of Materials

Research material obtained from individual participants includes questionnaires and interviews with study personnel, and urine samples. All data will be directly input into REDCap which is a secure, password protected web-based data collection system. The only written research material will be the informed consent and HIPAA documents. These paper records will be stored in an office in the Roper Medical Office Building (RMOB) that is locked when not in use. Urine samples will never be marked with any identifying information. They will be discarded once read.

c. Potential Risks and Risk Mitigation Strategies:

Potential risks of rTMS: The use of high frequency rTMS has been FDA approved for the treatment of major depressive disorder since 2008. Our stimulation parameters (3000 pulses, 10Hz, 5-Seconds on 10-Seconds off) are nearly identical to the FDA approved protocol (3000 pulses, 10Hz, 4-Seconds On, 8-Seconds off), and have been used safely in many investigations including those in depression (35), pain (12), and addictions (48, 52). We chose to use the slightly longer train duration of 5-seconds rather than 4-seconds due to its safety and efficacy in many trials including our preliminary single session trial with opiate users.

The common clinical dose of rTMS in depression is 36 treatments with 3000 pulses per treatment, for a total of 108,000 pulses (33). We will deliver a total of 18 treatments over 3 days with 3,000 pulses per treatment, for a total of 54,000 pulses. We subsequently will be giving a substantially lower total dose to each participant than is commonly given to patients being treated for depression. Accelerated treatment paradigms (including those with 6 treatments delivered daily) have been safely delivered in both depression (35-37, 62), and addictions (63, 64) populations without any clear adverse effect.

Risk of Seizure: The most serious risk associated with the use of rTMS is seizure. Since the adoption and widespread use of standard safety guidelines in 1997(65), there has only been one documented seizure with the type of rTMS we will deliver. The risk of seizure has been estimated to be less than 0.1% which is lower

than the risk of seizure associated with pharmacologic antidepressants(66). The risk of seizure is related to the various stimulation parameters (intensity, frequency, train duration), location of application, pre-existing risk of seizure, and substance/medication factors. In the very rare event a seizure is caused, removing the coil is typically sufficient to stop the seizure, and there is no increased risk of subsequent seizure. In order to mitigate the risk of seizure we will carefully individualize the intensity of stimulus (by performing a resting motor threshold determination), treat using standard treatment protocols (used safely in other studies), and exclude potential participants at higher risk of seizure (those with a past history of seizures, those in withdrawal from alcohol or benzodiazepines etc).

Risk of Site discomfort and headache: Two relatively common risks associated with the use of rTMS include the risk of mild transient site discomfort during treatment (most patients), and the risk of headache (Approximately 5%) following treatment. Both of these potential side effects are typically mild. In terms of mitigating site discomfort, we will slowly ramp up stimulation intensity during the first three sessions. In our experience both clinically and experimentally this is a successful strategy. Additionally, due to the anti-pain effect of rTMS, participants rapidly adjust to stimulation. In the unusual circumstance that a headache is caused by rTMS, over the counter analgesics are sufficient to alleviate the headaches, and will be available to patients on the inpatient unit.

Pain task: The pain task may cause discomfort but will not cause injury. The task will be stopped when it becomes painful to the participant.

Potential hearing loss: The discharge of the rTMS coil generates a high-energy click that may cause cochlear damage. Humans exposed to rTMS have shown temporary increases in auditory threshold (especially at high frequencies) lasting at least 5 minutes and less than 4 hours. Foam earplugs can protect against these changes and will be worn during rTMS sessions.

Safety in the case of pregnancy: This protocol will exclude pregnant women. Pregnancy status will be confirmed as part of the standard admissions process.

Potential risks of cue Induced craving paradigm: Drug cues are known to increase craving, and subsequently the use of an opiate cue paradigm will likely increase craving for opiates. The craving induced will be transient (22), with craving approaching baseline within 90 minutes. Additionally, it is unlikely our delivered craving paradigm will induce craving that is more intense than the individual cues that participants will encounter once they leave the hospital. Given that all of our drug cues will be given while patients are admitted to the inpatient unit, it is highly unlikely that the increased opiate craving produced by the opiate cue paradigm will result in any substance use. Our final cue-craving paradigm will be delivered on the day of discharge, however it will be done several hours prior to discharge, and we will closely monitor the craving response patients exhibit. Study staff will stay with each participant until their craving has returned to baseline levels. In the unlikely event that the individual has prolonged cue-induced craving, the P.I. will provide an appropriate referral.

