Integration of Study Procedures Into Inpatient Care: During inpatient care, standard treatment includes a combination of pharmacotherapy, psychotherapy, and social work interventions. Pharmacotherapy consists of detoxification from opiates (using a standardized protocol), and the use of medications to treat co-occurring conditions. During detoxification patients are assessed twice daily using the Clinical Opiate Withdrawal Scale (COWS) (57), and then undergo either a standardized buprenorphine taper (8mg x 2 days, 4mg x 3 days), or a standardized methadone taper (30, 25, 20, 15, 10, 5). Induction using either medication occurs at approximately 10am on the first morning of admission. On each of the following four days, medication is given at approximately 10am, and patients are discharged on the final day of their taper following their final dose of

medication. Currently there are no regular group therapy sessions, and regular meetings with individual therapists, social workers, and prescribers are less than 60 minutes in duration each.

The study has been designed specifically to not interfere with any aspect of the normal unit operations. One of the qualified study members will meet with interested patients once they are stable on buprenorphine/methadone, and no longer in acute withdrawal, subsequently the study will not interfere with the initiation of buprenorphine/methadone. Patients who would like to participate in the study, will be consented, enrolled, and will complete baseline assessments prior to starting treatment. The opiate cue craving paradigm, inhibitory control/delayed discounting paradigm, and the quantitative sensory testing will be completed on the morning after being induced on buprenorphine/methadone (before any rTMS), and the morning of the last dose of buprenorphine/methadone on the discharge day (after all rTMS has been delivered). Subsequently assessments will occur at the same time of day, and prior to patients taking buprenorphine/methadone, without disrupting the normal dispensing of medications (which is approximately 10am). Six 15 minute treatments will be delivered each of the next three days with approximately 30 minutes in between each treatment. Given that all standard treatment meetings (see above) occur in windows of less than 60 minutes, and rTMS will be delivered on the same floor as detoxification, study treatment will not interfere with any of the standard of care interventions participants receive.

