The study procedures will also not interfere with any of the standard of care pharmacotherapy commonly delivered during detoxification. There is no known added risk of rTMS during a buprenorphine/methadone taper (in our pilot trial several of our participants were stabilized on buprenorphine). The commonly used non-opiate medications including acetaminophen, hydroxyzine, and cyclobenzaprine, will be allowed during this study (but be held for at least 5 hours prior to each pain assessment). Patients being treated for OUD commonly have co-morbid symptoms of depression and anxiety (58). Subsequently, the initiation of antidepressant medications is common in the acute treatment setting, and will be allowed during this trial (and are commonly used safely with concurrent rTMS).

Inclusion Criteria:

- 1: Participants must be able to provide informed consent and function at an intellectual level sufficient to allow accurate completion of all assessment instruments.
- 2: Participants must meet DSM-5 criteria for moderate or severe OUD. While individuals may also meet criteria for use disorders of other substances (with the exception of alcohol or benzodiazepines), they must identify prescription opiates as their primary substance of abuse.
- 3: Participants must be admitted to the inpatient unit for opiate detoxification.
- 4: Participants must consent to random assignment.

Exclusion Criteria:

- 1: Participants who are pregnant will be excluded.
- 2: Participants with a history of/or current psychotic disorder will be excluded.
- 3: Participants with a history of dementia or other cognitive impairment will be excluded.
- 4: Participants with active suicidal ideation, or a suicide attempt within the past 90 days will be excluded.
- 5: Participants with contraindications to receiving rTMS (including a history of seizures, or any implanted metal above the neck) will be excluded.
- 6: Those with unstable general medical conditions will be excluded.
- 7: Those who are currently using naltrexone, or tramadol, will be excluded.
- 8: Those with alcohol or benzodiazepine use disorders will be excluded due to increased risk of seizure.

Schedule of Visits and Assessments:

	Assessment Domain	Baseline	Post	1 and 4 week F/U	3-Month SCRIPTS Review	
Screening and Enrollment Eligibility:						

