Mini International Neuropsychiatric Interview for the DSM-5 (MINI)(59): Structured interview to determine Axis I psychiatric conditions based on DSM-5 criteria.	Psychiatric History	х				
Patient Health Questionnaire Nine (PHQ9)(60): Self-Report measure of depressive symptoms.	Depressive Symptoms	х		х		
Time Line Follow Back (TLFB)(61) and Clinical Opioid Withdrawal Scale (COWS)(57): The TLFB is a validated measure quantifying drug use; average daily morphine equivalents will be calculated. The COWS is a validated measure quantifying withdrawal severity.	Opiate Use and Withdrawal	х				
Subjective Opioid Withdrawal Scale (SOWS) (68): The SOWS is a validated self-administered measure of opioid withdrawal.	Opiate Withdrawal	х	x			
The Barratt Impulsiveness Scale (BIS11) (69): The BIS is a validated questionnaire designed to assess the personality/behavioral construct of impulsivity.	Impulsivity	х				
The Pittsburgh Sleep Quality Index (PSQI) (70): Validated instrument used to measure the quality and patterns of sleep in adults.	Sleep	х		Х		
Work Productivity and Activity Impairment Questionnaire (71): The Work Productivity and Activity Impairment (WPAI) questionnaire is a well validated instrument to measure impairments in work and activities.	Functional Impairment	х		х		
The Rand 36 Item Short Form Health Survey (73): Validated self-report to assess quality of life.	Quality of Life	х		х		
Aim 1: Cue induced Craving: Primary ou paradigm.						
Prescription Opiate Craving Scale (21): Three item opiate craving scale. The three-item scale will also be administered at 1 and 4 week follow-	Provoked Opiate Craving	Х	X			

ups, but there will be no cue provocation.							
Aim 2: Pain Outcomes: Primary outcome: Change score in thermal pain threshold and pain tolerance.							
Mechanical, Thermal, and DNIC Pain Assessment: See description above.	Quantitative Sensory Assessment	x	x				
Brief Pain Inventory (23) and McGill Pain Questionnaire (24): Self report measures assessing severity, functional impairment, and affective components of pain. Administered daily during the acute phase of the study and at both follow-up visits.	Subjective Pain	х	x	x			
Exploratory Aims: Substance Use: Primary outcome: Abstinence over the final two weeks of the study, as defined by no self-reported use and a negative final urine drug screen. Executive function/inhibitory control: Will be measured using two validated computer tasks.							
Urine Drug Screen	Objective Substance Use	Х		x			

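### The seizure-risk text promises to exclude patients in alcohol or benzodiazepine withdrawal, but neither eligibility list names that exclusion

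*Combined protocol and SAP*

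**What the plan says.** The Risk of Seizure paragraph (Section E, 1.c, Potential Risks and Risk Mitigation Strategies) calls seizure the most serious risk of rTMS. It puts that risk below 0.1% and lists substance and medication factors among the things that affect it. One of its mitigation steps is to "exclude potential participants at higher risk of seizure (those with a past history of seizures, those in withdrawal from alcohol or benzodiazepines etc".

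The eligibility criteria appear twice, under Inclusion and Exclusion Criteria in Section D and again in Section E, 1.a, and the exclusion items are the same in both. The items that bear on this point are:

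- Exclusion 8: "Those with alcohol or benzodiazepine use disorders will be excluded due to increased risk of seizure".
- Inclusion 2, which makes the same exception: "While individuals may also meet criteria for use disorders of other substances (with the exception of alcohol or benzodiazepines").
- Exclusion 5: "Participants with contraindications to receiving rTMS (including a history of seizures, or any implanted metal above the neck) will be excluded".
- Exclusion 6: "Those with unstable general medical conditions will be excluded".

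On procedure, Section D (Integration of Study Procedures Into Inpatient Care) says patients are approached "once they are stable on buprenorphine/methadone, and no longer in acute withdrawal". It also says "During detoxification patients are assessed twice daily using the Clinical Opiate Withdrawal Scale (COWS"). The Schedule of Visits and Assessments adds the SOWS, a self-report scale of opioid withdrawal, and the MINI, described as "Structured interview to determine Axis I psychiatric conditions based on DSM-5 criteria".

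**The concern.** The risk text and the eligibility lists address the same hazard but define the excluded patients differently. The risk text names a state, withdrawal. Exclusion 8 names a diagnosis, use disorder. The two groups overlap but are not the same. A person can be withdrawing from a benzodiazepine taken as prescribed, for example, without meeting criteria for a use disorder. The risk text names that person for exclusion, and exclusion 8 does not.

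What is at stake is participant protection. The document describes a safeguard against what it regards as the gravest risk of the intervention, and the criteria used for screening do not state that safeguard. The timing makes this relevant, because stimulation begins early in the detoxification stay.

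**Working it through.** No sample-size, power or error-rate formula applies. The check is a comparison of the texts, with a short count of exposure.

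**Step 1. Trace each example in the risk text to the lists.**

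| Example in the Risk of Seizure text | Where it appears in both lists | Same rule? |
|---|---|---|
| Past history of seizures | Exclusion 5, named | Yes |
| Withdrawal from alcohol or benzodiazepines | Exclusion 8 and inclusion 2 name these substances, but as use disorders | No |

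The first example carries over unchanged. The second reappears with the same stated purpose, seizure risk, but with a different definition.

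**Step 2. Sort patients by the two definitions.**

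- Use disorder, in withdrawal: excluded by both texts.
- Use disorder, not in withdrawal: excluded by item 8. Here the lists are broader than the risk text, which leaves no safety gap.
- No use disorder, in withdrawal: excluded by the risk text but not by item 8.
- Neither: not affected.

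The gap is the third group only.

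**Step 3. Ask whether another step catches the third group.**

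- Exclusion 5 is open-ended because its two examples are introduced as inclusions. It could be read to cover this withdrawal, but it does not name it, and nowhere does the protocol define rTMS contraindications to include it.
- Exclusion 6 might apply if the withdrawal is judged an unstable medical condition. That too is an inference.
- The condition that a patient be out of acute withdrawal before being approached is tied to stability on buprenorphine or methadone, so in context it means opioid withdrawal.
- COWS and SOWS measure opioid withdrawal. No scale for alcohol or benzodiazepine withdrawal is described.
- The MINI establishes diagnoses. The Time Line Follow Back records use. The urine drug screen is scheduled at baseline, but its panel is not described.

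Nothing in this list catches the third group explicitly.

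**Step 4. Timing.** Induction is on the first morning of admission and baseline testing is the next morning, before any rTMS. Under the five-day buprenorphine taper (2 days + 3 days), post-treatment testing falls on the morning of day 5, after all rTMS. Three treatment days therefore fall on about days 2 to 4. Withdrawal from a substance stopped at admission could overlap with them. The documents do not say whether prescribed benzodiazepines are stopped at admission, so overlap is possible but not shown.

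**Step 5. Exposure.** 6 sessions per day x 3 days = 18 sessions. 18 x 3,000 pulses = 54,000 pulses, which matches the protocol's own total. Allocation is 20 active and 20 sham, and 20/40 = 0.5. If k such patients were enrolled, about k/2 would be expected to receive real stimulation. The documents give no basis for a value of k, which could be zero.

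**The case against.** The best reply is that the lists do more than item 8. Exclusion 5 covers contraindications in general, and the protocol itself treats this withdrawal as a seizure risk for rTMS, so a careful physician could exclude such a patient under item 5, or perhaps item 6. The risk text is also part of the same protocol, and its parenthesis ends in an open "etc", so it reads as an illustrative summary and not as a rival set of criteria. Recruitment is from one facility, and consent and enrolment are most often done by the principal investigator, who also performs every motor threshold assessment. Nothing shows that these staff would disregard the risk text.

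Much of this stands. A reader might infer that the lists exclude use disorders alone, that a patient in withdrawal passes every criterion, and that such patients will therefore be enrolled. The documents do not support that inference, because items 5 and 6 leave room to exclude them. Enrolment is a possible outcome, not an established one. Nor is there a flat contradiction: the texts are incompletely aligned.

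A reader might also object that item 8 has no time frame and could remove a patient with a long-remitted disorder. That makes the list more cautious and shows no safety gap.

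What the reply does not remove is that a named protection depends on inference. The list has an item written for these two substances and this risk, and a screener who turns to it finds a different rule.

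**Conclusion.** The point holds as an inconsistency in participant protection. The risk text names alcohol or benzodiazepine withdrawal as a ground for exclusion and neither eligibility list does. Only a reading of exclusion 5 or 6 would catch a patient in such withdrawal without a use disorder, and the opioid-focused withdrawal steps do not help.

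Its size cannot be stated as a number of patients. The affected group is narrow: no use disorder, actually in withdrawal when treated, and not excluded by judgement under item 5 or 6. The documents give no frequency for any of these. Of any such patients enrolled, about half would be expected to receive sham. The protocol's seizure figure of less than 0.1% is not specific to patients in withdrawal, so it neither measures nor dismisses the risk in this group.

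No endpoint, sample size, power statement or analysis is affected. The case for correcting it rests on the kind of risk and the ease of the correction, not on a demonstrated frequency. The conclusion assumes that the withdrawal condition before consent refers to opioids, as its context indicates.

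**What to change.** Reconcile the three places: the exclusion list in Section D, the exclusion list in Section E, 1.a, and the Risk of Seizure text in Section E, 1.c. The same seizure-risk exclusion should appear in both lists, within item 5 or item 8, and in the risk text. It should state whether it is defined by diagnosis, by withdrawal state, or by both, and it should be applied before randomisation. The clinical content is for the study physician to decide, and none is proposed here.

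The study physician should also confirm whether the baseline information already collected (MINI, Time Line Follow Back, urine drug screen) is enough to apply the agreed criterion. As described, these cover diagnoses and use, not alcohol or benzodiazepine withdrawal, so it should not be assumed that no further assessment is needed.

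The cost is a short amendment and possibly a few more screen failures, against about 400 opiate detoxification admissions in the past 12 months for 40 places. If a further assessment proves necessary, that would be an added cost.
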